### 8.3 Rescreening of Subjects

Rescreening of subjects is not allowed in this study.

## 9 TREATMENTS ADMINISTERED

## 9.1 Investigational Product(s)

## Test Product(s): **UNITY™ Vitreoretinal Cataract System (VCS)**

*Comparator Product(s) (If applicable):* Not applicable

[figure not shown]
**Table 9-1** **Test Product**

[figure not shown]
Test Product:	UNITY VCS consisting of: 1. Console including remote control and foot controller 2. UNITY Anterior Vitrectomy Kit 3. UNITY TOTAL PLUS Combined Procedure Pack 4. 25GA/27GA Entry System 5. High Performance Viscous Fluid Control Pack 6. 25GA/27GA TETRASpot Multi-spot Laser Probe 7. 27GA Illuminated Flexible Curved Laser Probe 8. 27GA Chandelier 9. 22GA Ozil Frag Pack 10. Ozil Frag Handpiece  [REDACTED]
Manufacturer:	Alcon Laboratories, Inc. [name]  [REDACTED]
Indication for use and intended purpose in the current study:	Indications for Use The Unity VCS, consisting of the console and compatible devices, is indicated for use during anterior and posterior segment ophthalmic surgery.  Intended Use The Unity VCS, consisting of the console and compatible devices, is intended to facilitate management of fluid and gases, as well as removal, grasping, cutting, illumination, and coagulation of ocular materials.
Product description and parameters available for this study:	The UNITY VCS in this study is a surgical instrument for use in anterior and posterior segment ophthalmic surgeries. The product's capabilities include driving a variety of surgical instruments that provide the ability to facilitate management of fluid and gases, as well as removal, grasping, cutting, illumination, and coagulation of ocular materials. Full product parameters are available for the current study.
Formulation:	N/A
Usage:	UNITY VCS will be used as directed in the user manual.
Packaging description:	Each UNITY VCS console and all compatible investigational devices will be packaged individually and have an investigational product specific serial or lot number.

Labeling description:	
Investigational labeling regulations apply for:
 

• UNITY VCS console

• Remote control

• Foot controller

• UNITY Anterior Vitrectomy Kit

• UNITY TOTAL PLUS Combined Procedure Pack

• 25GA/27GA Entry System

• High Performance Viscous Fluid Control Pack

• 25GA/27GA TETRASpot Multi-spot Laser Probe

• 27GA Illuminated Flexible Curved Laser Probe

• 27GA Chandelier

• 22GA Ozil Frag Pack

• Ozil Frag Handpiece

 
These devices will be labeled appropriately (e.g., “CAUTION – Investigational device. Limited by Federal [or United States] law to investigational use” or “Exclusively for Clinical Investigation” or “For Clinical Trial Use Only”). Each unit will be identifiable via a serial or lot number.

Training and/or experience requirements for device:	UNITY VCS should only be used by ophthalmic surgeons and operating room staff. It should only be operated according to the operating instructions as listed in the associated manuals.
Storage conditions:	
Temperature and humidity apply to room environmental conditions preceding and during device use.
 
Temperature:
 

• 10 to 35°C (50 to 95°F) Operating

• -10 to 55°C (14 to 131° F) Nonoperating

	Relative humidity: 10% to 95% without condensation See user manual for complete requirements and instructions.
Additional information:	Not applicable
Supply:	UNITY VCS and compatible devices will be shipped to the site by the sponsor. [REDACTED]
	Refer to the MOP for a detailed description.

More information on the test product can be found in the IB and directions for use for UNITY VCS.

### **9.3 Treatment Assignment/Randomization**

Only after signing the ICF, a subject will be assigned a subject number by the electronic data capture system.

All subjects who meet the inclusion/exclusion criteria and sign informed consent will undergo posterior segment surgery in without or with simultaneous cataract surgery with the UNITY VCS. Bias will be minimized as this is a single arm study. If both eyes qualify for the study, the study eye will be determined per investigator's discretion.

There will be no randomization of subjects.

### **9.4 Treatment Masking**

Not applicable as this is an open label, single arm study.

### **9.5 Accountability Procedures**

Upon receipt of IPs, the investigator or delegate must conduct an inventory of equipment and accessories by serial or lot number, complete study-specific confirmation of receipt procedures as described in the MOP and retain any required documentation in the investigator's clinical study records.

Throughout the study, the investigator or delegate must maintain records of IP use for each subject. This record must be made available to the study monitor for the purposes of verifying the accounting of IP supplies. Any discrepancies and/or deficiencies between the observed disposition and the written account must be recorded along with an explanation.

- All IPs sent to the investigator must be accounted for by study sponsor personnel, and in no case be used in an unauthorized manner.

- Refer to [Section 11](#) for additional information on the reporting of device deficiencies and to the MOP for information on return of IPs associated with these events.

The investigator is responsible for allowing de-installation of the provided UNITY VCS console, return of all unused devices, and proper discarding of all used devices as directed. Please refer to MOP for additional details.

## 9.6 Changes to Concomitant Medications, Treatments/Procedures

After the subject is enrolled into the study, the investigator must instruct the subject to notify the study site about:

- Any new medications
- Alterations in dose or dose schedules for current medications,
- Any medical procedure or hospitalization that occurred or is planned
- Any nondrug therapies (including physical therapy and blood transfusions).

The investigator must document this information.

## 10 STUDY PROCEDURES AND ASSESSMENTS

Study assessments will be obtained prior to vitreoretinal with or without simultaneous cataract surgery with the UNITY VCS and postoperatively at the study visits outlined below:

- Screening – Visit 0 (Day -30 to 0 prior to treatment)
- Surgery – Visit 00 (Day 0)
- 1 Day – Visit 1 (Day 1 to 3)
- 1 Week – Visit 2 (Day 4 to 10)
- 1 Month – Visit 3 (Day 16 to 44)
- 3 Month/Exit – Visit 4 (Day 76 to 104)

In addition to the scheduled visits listed above, the following visit may apply as needed:

- USV (completed when a treated subject reports for additional follow-up)
- Early Termination Visit (when subject would like to withdraw from the study participation)

Clinical assessments to be obtained at study visits are outlined in [Table 3-1](#) Schedule of Study Procedures and Assessments and are defined in the sections below.

## **10.1 Informed Consent and Screening**

The investigator or delegate must explain the purpose and nature of the study and have the subject read, sign, and date the IRB/IEC-approved informed consent document. The subject must sign the ICF BEFORE any study-specific procedures or assessments can be performed, including study-specific screening procedures. Additionally, have the individual obtaining consent from the subject and a witness, if applicable, sign and date the informed consent document.

The investigator or delegate must provide a copy of the signed document to the subject and place the original signed document in the subject's chart, or provide documentation as required by local regulations.

If a patient has reported for routine vitrectomy and/or cataract screening, then data obtained from the routine evaluation can be used for screening data as long as protocol requirements for timeframe (within 30 days of surgery) and required details have been met. Routine vitreoretinal and/or cataract screening data include, but are not limited to SLE, IOP, dilated pupil size, keratometry, biometry (ACD, AL), Snellen BCDVA with manifest refraction, and dilated fundus exam.

## **10.2 Description of Study Procedures and Assessments**

Study-specific procedures and assessments described here may include standard of care; other standard of care procedures performed in the clinical management of the subject are not excluded.

Detailed descriptions of assessments and procedures are provided in the MOP. The investigator is responsible for ensuring responsibilities for all procedures and assessments are delegated to appropriately qualified site personnel.

The enrollment on this study is competitive and once the target number of subjects is achieved, sponsor will close the enrollment.

### **10.2.1 Demographics**

Obtain demographic information including age, race, ethnicity, and sex.

### **10.2.2 Medical and Ocular History**

Collect medical history information, including information on all medications used within the past 30 days. Include herbal therapies, vitamins, and all over-the-counter as well as

prescription medications. Throughout the subject's participation, obtain information on any changes in medical health and/or the use of concomitant medications.

Medical history and concomitant medications will be collected in the eCRF as outlined in the MOP.

### **10.2.3 Adverse Event Collection: Safety Assessment**

Assess and record any adverse events that are observed or reported since the previous visit, including those associated with changes in concomitant medication dosing.

Note: AEs and device deficiencies must be recorded for all enrolled subjects from the time of signature of informed consent, regardless of subject enrollment status (screen failure or randomized).

### **10.2.4 Slit Lamp Biomicroscopy: Safety Assessment**

SLE of the cornea, iris/anterior chamber and lens must be performed before instillation of any diagnostic eye drops.

Refer to the MOP for grading scales for study specific assessments.

### **10.2.5 Device Deficiencies: Safety Assessment**

Assess and record any device deficiencies that are reported or observed since the previous visit. Requirements for reporting device deficiencies in the study can be found in [Section 11](#).

Note: AEs and device deficiencies must be recorded for all enrolled subjects from the time of signature of informed consent, regardless of subject enrollment status (screen failure).

### **10.2.6 Dilated Fundus: Safety Assessment**

Dilated fundus examination includes ophthalmoscopic assessments of the vitreous, retina, macula, choroid, and optic nerve.

### **10.2.7 Best Corrected Distance Visual Acuity: Safety Assessment**

Snellen visual acuity testing with manifest refraction must be performed prior to any assessment requiring administration of eye drops to dilate the eye, or any assessment requiring contact with the eye.

## **10.2.8 Intraocular Pressure: Safety Assessment**

Intraocular pressure must be measured using SOC.

## **10.2.9 Urine Pregnancy Test: Other Assessment**

A urine pregnancy test is required for female subjects of childbearing potential that are not postmenopausal or surgically sterile.

## **10.2.10 Keratometry: Eligibility Assessment**

Capture keratometry measurements of the central cornea using SOC. This assessment is required only when subjects are undergoing cataract surgery.

## **10.2.11 Pupil Size: Eligibility Assessment**

[figure not shown]
Measure dilated pupil size under photopic condition using SOC.

## **10.2.12 Biometry: Eligibility Assessment**

Perform biometry using SOC. Document the following: ACD, AL. This assessment is required only when subjects are undergoing cataract surgery.

## **10.2.13 Total Time in the Eye: Secondary Performance Assessment**

Obtain time from first entry into eye/first trocar into incision closure/last trocar out using a stopwatch.

## **10.3 Unscheduled Visits**

[figure not shown]
An Unscheduled Visit (USV) is defined as follows:

- Ocular examination that is not SOC and not required by the protocol
- Examination conducted by the study staff
- New findings, or change to a previous finding was discovered

If a subject visit occurs between any regularly scheduled visit and the visit is conducted by study personnel, this visit must be documented as an Unscheduled Visit. If the subject seeks medical attention outside the clinic (for example, at an emergency room) or at the clinic but is seen by non-study personnel, the investigator is to capture adverse event-related information on the adverse event form upon becoming aware.

During all unscheduled visits, the investigator must conduct the following procedures:

- Collect adverse event information, if applicable
- Collect device deficiency information, if applicable
- Collect SSI information, if applicable
- Record changes in medical condition or concomitant medication

The investigator may perform additional procedures for proper diagnosis and treatment of the subject. These include but are not limited to those noted in [Table 3-1](#) Schedule of Study Procedures and Assessments. The investigator must document this information in the subject's case history source documents.

If during a USV the subject is discontinuing from the study, the investigator must conduct Exit procedures according to [Table 3-1](#) Schedule of Study Procedures and Assessments and Section [10.4.3](#), as possible.

## 10.4 Discontinued Subjects

### 10.4.1 Screen Failures

Subjects who were excluded from the study after signing the informed consent and prior to exposure to IP.

The investigator must document the reason for screen failure in the subject's case history source documents.

Subject numbers must not be reused.

### 10.4.2 Discontinuations

Discontinued subjects are individuals who voluntarily withdraw or are withdrawn from the study by the investigator after signing informed consent, meeting eligibility criteria, and are exposed to IP.

Subject numbers of discontinued subjects must not be reused (i.e., subject replacement is not allowed).

Subjects may discontinue from study or study treatment at any time for any reason. Subjects may also be discontinued from study treatment at any time if, in the opinion of the investigator, continued treatment poses a risk to their health.

For subjects choosing to discontinue from the study after exposure to IP, the investigator must complete all Exit procedures according to [Table 3-1](#) Schedule of Study Procedures and Assessments, if the subject is willing and able, and if in the opinion of the investigator it is safe for the subject to do so.

The investigator must document the reason for study or treatment discontinuation in the subject's case history source documents.

To ensure the safety of all subjects who discontinue early, investigators must assess each subject and, if necessary, advise them of any therapies and/or medical procedures that may be needed to maintain their health.

### **10.4.3 Schedule of Procedures and Assessments for Subjects Discontinued from Investigational Product**

If a subject discontinues from study treatment, every effort must be made to keep the subject in the study and to continue with the study assessments as specified in the schedule of study procedures and assessments until the final visit.

## **10.5 Clinical Study Termination**

The study sponsor reserves the right to suspend or close the investigational site or suspend or terminate the study in its entirety at any time.

If the clinical study is prematurely terminated or suspended by the study sponsor:

- The study sponsor must:
  - Immediately notify the investigator(s) and subsequently provide instructions for study termination.
  - Inform the investigator and the regulatory authorities of the termination/suspension and the reason(s) for the termination/suspension.
- The investigator must:
  - Promptly notify the IRB/IEC of the termination or suspension and of the reasons.
  - Provide subjects with recommendations for poststudy treatment options as needed.

The investigator may terminate the site's participation in the study for reasonable cause.

### **10.5.1 Follow-up of Subjects after Study Participation has Ended**

Following this study, the subject will return to their eye care professional for their routine eye care.

[figure not shown]
## **11 ADVERSE EVENTS AND DEVICE DEFICIENCIES**

### **11.1 General Information**

An AE is any untoward medical occurrence, unintended disease or injury, or untoward clinical signs (including abnormal laboratory findings) in subjects, users, or other persons, whether or not related to the investigational medical device (test product). Refer to the [Glossary of Terms](#) and figures below for categories of AEs and SAEs.

**Figure 11-1**

**Categorization of All Adverse Events**

\*In this study, only AEs related to the IP/device (i.e., UNITY VCS) are considered as device related ADE.

### **Specific Events Relevant to this Protocol**

In addition to reporting all AEs (serious and nonserious) meeting the definitions, the investigator must report any occurrence of the following as an SAE including but not limited to:

#### ***Serious Adverse Events***

- Corneal incision site leakage
- Sclerotomy site leakage

- Toxic anterior segment syndrome
- Posterior capsular tear
- Vitreous prolapse
- Iridodialysis
- Iatrogenic retinal tear
- Chronic corneal edema (corneal stromal or epithelial swelling resulting in BCDVA of  $\leq 20/40$  at  $\geq 1$  month)
- Clinically significant cystoid macular edema
- Uncontrolled increase in IOP  $\geq 10$  mmHg over baseline and at least 25 mmHg
- Endophthalmitis
- Retinal detachment
- Retinal vascular occlusion
- Pupillary block
- Suprachoroidal hemorrhage
- Vitreous hemorrhage
- Secondary surgical intervention (excluding posterior capsulotomy, planned surgical intervention such as laser photocoagulation and silicone oil removal)

NOTE: Wound burps during the first week postoperatively, suture removal, planned surgical interventions such as blepharoplasty, laser photocoagulation, silicone oil removal, and Nd:YAG capsulotomy (for PCO) are not considered adverse events for this study.

AEs occurring in association with a device that is used in conjunction with the UNITY VCS (e.g. gas, and silicone oil) will be classified separately from those associated with the investigational device itself. Expected complications from use of femtosecond laser-assisted procedures as noted in [Section 5.3](#) and additional medical interventions (e.g. ocular injections) will not be considered device related AEs.

In addition, aqueous cells and flare, corneal edema, eye redness, raised IOP, subconjunctival hemorrhage, and superficial punctate keratitis are examples of early postop findings that are typically observed following ocular surgery. These are not considered AEs if they can be reasonably expected to resolve within 2 weeks and not result in any untoward long term visual outcome impact.

Any other potentially sight-threatening event may also be considered serious based on the judgment of the investigator and should be reported appropriately as delineated in Section [11.3](#).

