Serious Adverse Event (SAE)	
Adverse event that led to any of the following:
 

• Death.

• A serious deterioration in the health of the subject, users or other persons as defined by one or more of the following:

a) a life-threatening illness or injury Note: Life-threatening means that the individual was at immediate risk of death from the event as it occurred, i.e., it does not include an event which hypothetically might have caused death had it occurred in a more severe form.

b) any potentially sight-threatening event or permanent impairment to a body structure or a body function including chronic diseases.

c) inpatient hospitalization or prolonged hospitalization.

d) a medical or surgical intervention to prevent a) or b). This includes any ocular secondary surgical

	
intervention excluding posterior capsulotomy.
 

e) any indirect harm as a consequence of incorrect diagnostic test results when used within manufacturer's instructions for use.

• Fetal distress, fetal death, congenital abnormality or birth defect including physical or mental impairment.

 
Note: Planned hospitalization for a preexisting condition, or a procedure required by the CIP, without serious deterioration in health, is not considered a serious adverse event.
 
Refer to Section 11 for additional SAEs.

Serious Health Threat	
Signal from any adverse event or device deficiency that indicates an imminent risk of death or a serious deterioration in the health in subjects, users, or other persons, and that requires prompt remedial action for other subjects, users, or other persons.
 
Note: This would include events that are of significant and unexpected nature such that they become alarming as a potential serious health hazard or possibility of multiple deaths occurring at short intervals.

Study Start	The start of the study is considered to coincide with the enrollment of the first patient.
Study Completion	The completion of the study is considered to coincide with the study-level last subject last visit or the decision to terminate the trial, whichever is later.

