## 6.4 Safety Objective(s)

Table 6-2

Safety Objective(s)

Objective(s)	Endpoint(s)
To obtain device-specific safety clinical data	

• Ocular and nonocular AEs and SAEs

• Device deficiencies

• Secondary surgical interventions

• Unplanned intraoperative procedures

[figure not shown]

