#### ***Causality***

Related	An AE classified as related may be either definitely related or possibly related where a direct cause and effect relationship with the medical device or study procedure has not been demonstrated, but there is a reasonable possibility that the AE was caused by the medical device or study procedure.
Not Related	An AE classified as not related may either be definitely unrelated or simply unlikely to be related (i.e., there are other more likely causes for the AE).

The study sponsor will assess the AEs and may upgrade the investigator's assessment of seriousness and/or causality. The study sponsor will notify the investigator of any AEs that are upgraded from nonserious to serious or from unrelated to related.

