5.3.1 Ocular and Nonocular AEs and SAEs

All adverse events reported to Alcon will be accounted for in the reporting. Descriptive summaries (counts and percentages) and listings will be presented. The type of event (serious, device related, etc.) will be summarized overall and by ocular/non-ocular status. Events will also be summarized by MedDRA preferred term, with the number and percent of subjects and a 95% exact binomial confidence interval, as well as a count of the number of events. The applicable definition of an adverse event is in the study protocol. A listing of all adverse events will be constructed to provide further details.

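### Protocol 11.1 leaves seriousness optional for unlisted sight-threatening events that the glossary already defines as SAEs

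*Protocol*

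**What the plan says.** Two places in the protocol decide whether a sight-threatening event is serious.

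- **Glossary, Serious Adverse Event, criterion b.** The definition covers "any potentially sight-threatening event or permanent impairment to a body structure or a body function including chronic diseases". An event of that kind is an SAE; no further step of judgment is attached.
- **Section 11.1, Serious Adverse Events.** After 17 listed items that must be reported as SAEs, the text adds: "Any other potentially sight-threatening event may also be considered serious based on the judgment of the investigator".

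Two further passages say how these relate. The glossary entry ends by sending the reader to Section 11 "for additional SAEs". The lead-in to the Section 11.1 list opens with "In addition to reporting all AEs (serious and nonserious) meeting the definitions".

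On review, the Causality text says: "The study sponsor will assess the AEs and may upgrade" the investigator's assessment of seriousness or causality. SAP 5.3.1 summarises events by type, including serious, and says: "The applicable definition of an adverse event is in the study protocol". It gives no SAE definition of its own and does not say whether the investigator's or the sponsor's classification is tabulated.

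**The concern.** The same kind of event is serious by definition in one place and optionally serious in another. An investigator who follows 11.1 literally can accept that an event threatens sight and still file it as nonserious.

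Two things are at stake. First, "Ocular and nonocular AEs and SAEs" is a listed safety endpoint. There is no control arm, and Protocol 7.2 intends to set the results against existing evidence on these surgeries. That comparison rests on the absolute SAE rate and on a clear definition behind it. Second, Section 11.3 ties the 24-hour report to the classification: it covers SAEs and adverse device effects, so an event that is labelled neither falls outside it.

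**Working it through.** The plan states no SAE rate, so there is no figure to reproduce. The check is mainly a comparison of texts.

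**1. Which rule governs?** The glossary describes Section 11 as a source of additional SAEs, and the 11.1 lead-in places its list on top of events that already meet the definitions. Neither narrows criterion b, so the glossary rule stays in force and the *may* sentence conflicts with it.

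**2. What does the *may* sentence leave to judgment?** Its subject is an event already described as potentially sight-threatening; what it leaves open is whether that event is serious. Criterion b leaves open only whether the event is potentially sight-threatening.

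**3. In which direction can it act?** Every event it covers is an SAE under criterion b. Using the discretion can therefore remove SAEs from the count but cannot add any.

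**4. Which events are affected?** An event must pass all of these filters:
- it is not among the 17 listed items, which include endophthalmitis, retinal detachment, retinal vascular occlusion, suprachoroidal hemorrhage, vitreous hemorrhage and unplanned secondary surgical interventions;
- it meets no other glossary criterion (death, life-threatening illness, permanent impairment, hospitalization, an intervention to prevent impairment, and so on);
- it is recognised as potentially sight-threatening but filed as nonserious;
- the sponsor does not upgrade it.

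To escape the 24-hour report it must also be judged not device-related.

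**5. What does one reclassified subject do to the rate?** One eye per subject is studied, so eyes and subjects coincide. Protocol 8 targets 100 treated subjects: 1/100 = 1.0 percentage point. If 120 enrol and 10% fail screening, 120 × 0.9 = 108 are treated, and 1/108 = 0.93 points. This applies only to a subject with no other SAE.

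**6. Illustration on assumed counts.** None of these counts comes from the documents. With n = 100 and exact (Clopper-Pearson) 95% intervals:

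| Subjects with an SAE under either rule | Extra subjects serious only under criterion b | Rate under criterion b (95% CI) |
|---|---|---|
| 5 | 0 | 5.0% (1.6 to 11.3) |
| 5 | 1 | 6.0% (2.2 to 12.6) |
| 5 | 3 | 8.0% (3.5 to 15.2) |
| 10 | 0 | 10.0% (4.9 to 17.6) |
| 10 | 1 | 11.0% (5.6 to 18.8) |
| 10 | 3 | 13.0% (7.1 to 21.2) |

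The intervals overlap heavily. The table shows scale only; nothing in the documents says how many subjects belong in the middle column.

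**The case against.** The case on the other side is substantial.

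- **The sentence may be meant as a catch-all**, with judgment applying to whether an unlisted event qualifies at all. That may be the intent, but the wording takes the sight threat as given and leaves seriousness open. If the narrower meaning was intended, the fix simply states it.
- **Judgment remains under either rule.** The protocol does not define what counts as potentially sight-threatening, so an investigator inclined to under-call can do so at that step. This stands: the fix closes only the gap between recognising the threat and calling the event serious.
- **Few events are affected.** This also stands, given the 17 listed items and the remaining glossary criteria.
- **Nothing is hidden.** An event filed as nonserious still appears in the preferred-term summary of SAP 5.3.1 and in the AE listing. This stands. What changes is its label and possibly its reporting speed.
- **The sponsor assesses all AEs.** True, but upgrading is optional and no criterion for it is given.

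A reader might go further and infer that the SAE rate will be materially understated, perhaps by a sixth to a third. The documents do not support this: any such fraction only restates assumed counts. Nor do they make the SAE rate the main safety result, since it is part of one of four unranked safety endpoints with no hypotheses. A reader might also infer bias from lack of masking. Protocol 9.4 says: "Not applicable as this is an open label, single arm study". With one arm there is no between-arm contrast to distort. That practice will differ between sites, or that the operating surgeon makes the call, is likewise not stated.

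**Conclusion.** The two passages contradict each other, and the text is wrong as written, but the point is minor. The permissive sentence in 11.1 lets an event that is an SAE by definition be filed as nonserious. The effect can run only towards fewer SAEs and, when the event is also judged not device-related, takes it out of the 24-hour report.

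The size is about 1 percentage point per reclassified subject, on the assumption of about 100 treated eyes and no other SAE in that subject. How many subjects would be reclassified cannot be derived from the documents; given the breadth of the mandatory list, it is probably few. The conclusion rests on reading Section 11 as adding to the glossary, which both cross-references support.

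**What to change.** Reconcile the glossary and Protocol 11.1 by rewording the one sentence in 11.1. It should say that any other event the investigator judges to be potentially sight-threatening meets SAE criterion b and must be reported as an SAE under 11.3. The investigator then decides only whether sight is potentially threatened.

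In SAP 5.3.1, state that SAEs are tabulated under that single definition. It would help to add, in the same sentence, whether the investigator's or the sponsor's final classification is used.

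The cost is one protocol sentence and one SAP sentence. No visit, treatment or sample size changes. The downside is possibly a few more SAE reports and a slightly higher reported SAE rate.
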